2.6. Imputation Rules for Missing and Partial Dates

In general, imputation of missing dates will be made for AE onset date, AE resolution date, date of death, start and end dates of concomitant and subsequent therapies, and date of initial diagnosis according to the following rules. Start date will be imputed before end date.

- If date is completely missing, no imputation will be made.
- If year is missing, no imputation will be made.
- If only year is present but month and day are missing, then June 30th will be used.
- If only day is missing but year and month are available, then the 15th of the month will be used.

However, the above imputations will be modified by the following rules:

- If such imputed date for initial diagnosis is on or after the first dose date, then the first dose date - 1 will be used.
- The imputed start date for subsequent therapies will be adjusted sequentially using the following steps:
 - If the imputed start date is before the treatment discontinuation date (or last dose date if no treatment discontinuation date) but in the same year and month, then the treatment discontinuation date (or last dose date if no treatment discontinuation date) will be used.
 - If subsequent therapy end date is not missing and is before the imputed subsequent therapy start date, then the subsequent therapy end date will be used as the start date.
- If the imputed date is for a date of death and is before the last date that the subject is known to be alive, the latter date will be used.
- The imputed AE start date will be adjusted sequentially using the following steps:
 - If the imputed date is in the same year and month as but day before the first dose date, then the first dose date will be used, or if it is in the same year and month as but day after the last dose date + 30 days, then the last dose date + 30 days will be used.
 - If AE end date is not missing and the imputed AE start date is after the AE end date, then the AE end date will be used.
 - If the imputed AE start date and is after date of death, then date of death will be used
 - If the imputed AE start date is in the same month and year but after the 1st subsequent therapy start date, then 1st subsequent therapy start date will be used.
- If the imputed date is for an AE end date and is after the death date, then the death date will be used, or if the imputed AE end date is before the AE start date, then the AE start date will be used.

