6.1.2. All Adverse Events

Treatment-emergent AEs (TEAEs) are defined as 1) those that first occur in TEAE period (defined as the time from first dose date through 30 days after last dose date, or day before subsequent anticancer therapy, whichever occurs first); 2) present before first dose, but worsened in toxicity grade during TEAE period; 3) had missing start date and its end date is during the TEAE period; 4) was a drug-related event. To determine TEAE, partially missing AE start dates will be imputed according to the rules stated in section 2.6.

Treatment-emergent AEs will be summarized by system organ class and preferred terms, by NCI toxicity grade, by relationship to erdafitinib, and by action taken.

The severity of AEs will be graded on a scale of 1 to 5 according to the adult NCI Common Terminology Criteria for Adverse Events (NCI-CTCAE version 5.0 or higher) where higher grades indicate events of higher severity.

For each TEAE, the percentage of subjects who experience at least 1 occurrence of the given event will be summarized. Tables will be sorted by frequency in incidence (the highest to lowest incidence).

For subjects using strong CYP3A inhibitor during treatment-emergent period, all TEAEs will be summarized by SOC, PT, maximum severity, and strong CYP3A inhibitor (Yes vs No). For subjects using strong CYP2C9 inhibitor during treatment-emergent period, all TEAEs will be summarized by SOC, PT, maximum severity, and strong CYP2C9 inhibitor (Yes vs No).

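### SAP 2.6 resets a partial AE onset to the day new therapy starts, one day after the TEAE period closes, so the reset never brings an event into the window; SAP 6.1.2 item 3 leaves a related gap for wholly missing start dates

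*SAP*

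**What the plan says.** SAP 6.1.2 gives the TEAE period as "defined as the time from first dose date through 30 days after last dose date, or day before subsequent anticancer therapy, whichever occurs first". It then links the classification to the imputation rules: "To determine TEAE, partially missing AE start dates will be imputed according to the rules stated in section 2.6".

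SAP 2.6 sets two defaults. With the day missing: "If only day is missing but year and month are available, then the 15th of the month will be used". With month and day missing: "If only year is present but month and day are missing, then June 30th will be used". A date with no year, or no date at all, is not imputed.

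The imputed AE start is then adjusted in sequence. An onset in the first-dose month but before first dose moves to the first dose date. An onset in the same month as, but "after the last dose date + 30 days, then the last dose date + 30 days will be used". An onset later than a known AE end date moves back to that end date, and one later than death moves to the death date. Last comes the new-therapy step: an onset "in the same month and year but after the 1st subsequent therapy start date, then 1st subsequent therapy start date will be used".

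For an AE with no start date, item 3 of the TEAE definition counts it if it "had missing start date and its end date is during the TEAE period". Item 4 counts any drug-related event whatever its date.

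**The concern.** The first-dose and last-dose adjustments both place an uncertain onset on a day that belongs to the TEAE period. The new-therapy step places it on the first day that does not. It acts only on dates already beyond the window and leaves them beyond it, so it can never change TEAE status, which is the purpose 6.1.2 gives for the imputation. This looks like an off-by-one in drafting.

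Item 3 has a similar effect by a different route. An AE with no start date and no end date cannot satisfy items 1 to 3, even if the subject is still taking erdafitinib.

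Incidence and severity of AEs is a secondary endpoint (Protocol Section 3), and the trial has one arm (SAP 1.5), so absolute incidence is the safety result. The tables of all, serious, Grade 3 or worse, discontinuation and fatal events are built on TEAEs (SAP 6.1.1). Because item 4 protects drug-related events, any loss falls on events judged not related, in the all-causality tables.

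**Working it through.** The documents give no figure on this point, so the check runs the date rules directly.

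**Inputs.** L = last dose, T = start of first subsequent therapy.
- Window end (SAP 6.1.2): W = min(L + 30, T − 1).
- Default onset (SAP 2.6): the 15th, or 30 June if only the year is known.
- Adjustments in the order listed in SAP 2.6.
- Assumptions: a 30-day month, first dose in an earlier month, no known AE end date. The documents do not give the gap from L to T. Gaps of 1, 7, 14, 21 and 28 days were tried and gave identical results.

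**1. One case.** L = 27 May, T = 10 June, onset recorded as June.
- L + 30 = 26 June; T − 1 = 9 June; W = 9 June.
- Default 15 June is after 10 June, so it is reset to 10 June.
- 10 − 9 = 1 day outside. Without the step it would be 15 − 9 = 6 days outside. The event is out either way.

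**2. The parallel step.** L = 10 May, no new therapy, onset June. L + 30 = 9 June, so 15 June is reset to 9 June, the last day inside. The event counts, although 21 of the 30 June days lie after the window.

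**3. All therapy start days d = 1 to 30, day missing.**

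| Quantity | Result |
|---|---|
| Step fires | d = 1–14 (14 of 30) |
| Imputed date outside, SAP text | d = 1–15 (15 of 30) |
| Imputed date outside, no step at all | d = 1–15 (15 of 30) |
| Outside although an in-window onset was possible | d = 2–15 (14 of 30) |

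On d = 15 the default equals therapy start, so the word *after* stops the step firing, yet the date is still outside. The same happens when the therapy's own start day is missing and is also set to the 15th. From d = 16 the 15th is inside.

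Share of the month before therapy = (d − 1)/30: d = 2 gives 1/30 = 3%; d = 14 gives 13/30 = 43%; d = 15 gives 14/30 = 47%. Summed over start days, 1 + 2 + … + 14 = 105 of the 0 + 1 + … + 29 = 435 possible in-window combinations of therapy day and onset day are classified out: 105/435 = 24%.

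**4. Year only.** The default is 30 June. The step fires for therapy on 1–29 June, and on 30 June the two dates coincide. All of these are outside. If therapy starts before June, the same-month condition means the step does not apply; this point does not extend to that case.

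**5. Events that still count.**
- Drug-related AEs (item 4).
- AEs with a known end date before therapy: in case 1, an end date of 8 June moves the start to 8 June, inside.
- Cases where L + 30 falls before therapy: L = 6 May, T = 10 June, onset June. The date is reset to 5 June, the new-therapy step does not fire, and 5 June is inside.

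**6. Item 3.** Compare two not-related AEs with no start date. One resolves on a day inside the window and counts. The other continues through treatment, has no end date, and does not. Neither onset is known, and the longer event is the one dropped.

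**7. After the change.** Using the day before therapy, triggered on or after therapy start and kept within the reported month, the imputed date is inside for 29 of 30 therapy start days, against 15 of 30. The remaining day is therapy on the 1st, when no day of that month is in the window.

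**The case against.** The strongest reply is that the SAP's answer is often the likelier one. With the day missing and therapy on days 2 to 15, the share of the month on or after therapy runs from 16/30 = 53% to 29/30 = 97%. Counting all such events would include some that began under another anticancer drug. That is true and is a cost of the change. But the SAP already takes the inclusive side at its other boundary: in step 2 of the working it counts an event when 70% of the month (21/30) lies after the window. The new-therapy step departs from the SAP's own convention.

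A second reply is that partial dates should be rare here. Protocol 8.1.3 asks for the End-of-Treatment Visit before any subsequent cancer treatment, so an AE present by then should be seen at a dated visit, and sites can be queried. Deaths up to 30 days after last dose are summarised separately (SAP 6.1.4). This limits the number of events but does not align the two sections.

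A third reply is that item 3 is a stated convention and contradicts no other section. That is correct. The case against it rests on its result for ongoing events.

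A reader might infer that the step removes events from the TEAE tables, or that every AE with a partial date in the therapy month is lost. The documents support neither. The same 15 of 30 start days are outside with or without the step, and the exceptions in step 5 of the working keep many events in.

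**Conclusion.** The mismatch between SAP 2.6 and 6.1.2 is real: the new-therapy adjustment cannot do its job as written. The events left out meet all of these conditions: judged not related; no known end date before the new therapy; that therapy starts within 30 days of last dose; and the imputed onset is on or after it. With the day missing, this means therapy on days 2 to 15, when 3% to 47% of a 30-day month precedes therapy. With only the year known, it means therapy in June, up to the 30th. These shares count calendar days. Reading them as probabilities would assume that onset is equally likely on each day.

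The item 3 gap is separate: not-related AEs with a wholly missing start date are left out if they are ongoing or end after the window, including in subjects still on treatment.

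Both rules can only lower the counts in the all-causality tables. A material understatement of toxicity should not be inferred: the number of such AEs cannot be computed from the documents and is probably small. No efficacy result is affected. The change is worth making because the classification is wrong as written and the correction is cheap.

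**What to change.** **SAP 2.6, AE start date, last step.** If the imputed start is on or after the first subsequent therapy start in the same month and year, use the day before that therapy. The date must not precede the first dose date, nor the first day of the reported month (or of the reported year, if only the year is known). The on-or-after trigger covers therapy on the 15th and on 30 June. The floor stops an AE recorded in June from being dated 31 May when therapy starts on 1 June.

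**SAP 6.1.2, item 3.** Treat an AE with a wholly missing start date as treatment-emergent unless its end date is before the first dose.

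**Cost.** Two SAP phrases and a derivation update, with no change to conduct, data collection or efficacy analysis. TEAE counts may rise slightly and may include some events that began after the new therapy or, under item 3, before the first dose. SAP 2.6 applies the AE rule to concomitant medication as well, so the text should say whether the new step carries over to it.

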3. INTERIM ANALYSIS AND DATA REVIEW COMMITTEE

3.1. Data Review Committee (DRC)

A DRC will be established for monitoring of safety data and for review of interim efficacy data, to ensure the safety of the subjects enrolled in this study, and to assess efficacy objectives. This committee will consist of at least one medical expert and at least one statistician; committee membership responsibilities, authorities, and procedures will be documented in the DRC charter.

After each review, the DRC will make recommendations such as:

- The continuation of the study
- The continuation of enrollment in specific tumor histologies
- The allowance of more enrollment above the cap 30 on a tumor histology or multiple tumor histologies
- The early success of the study

Details of the composition of the DRC and their operational procedures will be specified in the DRC Charter.

3.2. Interim Analysis (Broad Panel Cohort)

Three interim futility analyses are planned for the Broad Panel Cohort when approximately 30%, 50%, and 70% of the subjects in the Broad Panel Cohort (ie, approximately 60, 100, and 140 subjects) have been treated and are considered response-evaluable by investigator assessment, irrespective of the tumor histologies and the subject distribution among the tumor histologies ([Figure 2](#), N represents the number of response-evaluable subjects). The tumor histology list for interim futility analysis is pre-defined in [Table 3](#) (except for the group Other including all other tumor histologies not listed). In addition, an interim efficacy analysis will be conducted for the Broad Panel Cohort at the same time as the second interim futility analysis, [Figure 2](#). An early success may be declared if the observed ORR by IRC is 50% or higher with consistent effect across histologies. Regardless of the outcome of the interim efficacy analysis, study enrollment will continue to better characterize the efficacy for the active tumor histologies. The DRC will review the data from the interim analyses (e.g. efficacy, safety, biomarker etc.) and make recommendations to the study team.

The Treated Population in the Broad Panel Cohort will be used to summarize interim population characteristics and safety; the Safety Analysis Set (combining the Broad Panel Cohort, Cholangiocarcinoma Expansion Cohort, Exploratory Cohort and the Pediatric Cohort) will also be used for safety evaluation; the Response-evaluable Population (a subset of the Treated Population) in the Broad Panel Cohort will be used for the interim futility analysis, unless otherwise specified.

For interim analysis, disease progression and response evaluation based on investigator assessment using RECIST v1.1. or RANO will be primarily used to allow quick decisions; however, evaluation based on available IRC assessment may also be provided as supportive data. Note that

[figure not shown]
for Interim II, if an early success is to be declared, disease progression and response will be primarily based on IRC assessment.

A Statistical Support Group (SSG), independent of the study team, will support the interim analyses. The SSG will prepare preplanned outputs in Adaptive Clinical Trials Integrated Virtual Environment (ACTIVE) for the futility analysis report, which will be based on overall response rate (ORR) by investigator assessment using a Bayesian hierarchical model, implemented in FACTS v6.2 Enrichment Design-Dichotomous engine (Berry 2013, Chugh 2009). The BHM borrows information across tumor histologies and allows for evaluation of each tumor histology individually given the often-unique features of each group (details in [Appendix A.1](#)). At least 5 response-evaluable subjects in a tumor histology are required for the futility analysis. The futility guideline will be based on the posterior probability of $ORR > 25\%$ in the Broad Panel Cohort for a given tumor histology with a threshold of 40%, i.e., a tumor histology meets the model-based futility criteria if the posterior probability $Pr(ORR > 25\%) < 40\%$. The operating characteristics of the BHM under different scenarios are detailed in [Appendix A.3](#). For Interim II and III, the futility assessment takes into consideration of more available data from subjects included in previous futility analysis (including the subjects in early futile tumor histologies if applicable) as well as data from newly enrolled subjects after previous interim analysis. In addition, during Interim II and III, histologies that stopped for futility in previous assessment will only be included for BHM information borrowing but will not be assessed for futility again. Note that the group Other will be included in the BHM evaluation for information borrowing only but will not be deemed futile early and will continue enrollment until cap is reached.

Besides the BHM based futility guideline, all available interim data (eg, efficacy, safety, and biomarker data) will be assessed to determine whether enrollment in a given tumor histology should continue, such as the representativeness of biomarker alterations (the expected variant representation by tumor histology based on genomic database assessment). If a tumor histology is deemed futile by the DRC, further enrollment in the histology group will stop; subjects who have been enrolled in the tumor histology group will continue treatment and evaluation as per the protocol. Note that in the primary analysis, a final futility assessment using the same futility guideline as at the interim (i.e, posterior $Pr(ORR > 25\%) < 40\%$) but based on ORR by IRC will be performed for all enrolled tumor histologies as part of the primary analysis to identify the tumor histologies for the pooled primary efficacy analysis (Details in section [5.2.3](#)).

Other details of the planned analysis and efficacy/futility assessment are specified in Section [4-6](#).

Figure 2: Interim Analysis for the Broad Panel Cohort

*At Interim Analysis II, both futility and efficacy will be assessed.

4. SUBJECT INFORMATION

4.1. Demographics and Baseline Characteristics

Subject demographics and baseline disease characteristics will be summarized in [Table 4](#).

Table 4: Demographic Variables

Continuous Variables:	Summary Type
Age (years)	Descriptive statistics (N, mean, standard deviation [SD], median and range [minimum and maximum]).
Weight (kg)	
Categorical Variables	
Age (≥ 6 to < 12 years (applicable to the Pediatric Cohort only), ≥ 12 and < 18 years, ≥ 18 and < 65 years, ≥ 65 years)	
Sex (male, female, undifferentiated)	
Race ^a (American Indian or Alaska Native, Asian, Black or African American, Native Hawaiian or other Pacific Islander, White, Other, Multiple)	Frequency distribution with the number and percentage of subjects in each category.
Ethnicity (Hispanic or Latino, not Hispanic or Latino)	
Geographical Region (North America, Europe, Rest of the World)	

^aIf multiple race categories are indicated, the Race is recorded as 'Multiple'

Table 5: Baseline Characteristics

Continuous Variables:	Summary Type
Time from initial diagnosis to first dose (months)	Descriptive statistics (N, mean, standard deviation [SD], median and range [minimum and maximum]).
Hematology	
Hemoglobin	
Chemistry	
Creatinine Clearance	
Categorical Variables	Frequency distribution with the number and percentage of subjects in each category.
Performance Status*	
Metastatic disease sites	
Visceral metastasis	
Number of body sites with metastatic disease	
Prior Radiotherapy	
Prior Systemic Therapy in advanced/metastatic setting	
Prior Cancer-Related Surgery/Procedure	
Number of prior lines of anticancer therapies (1, 2 or ≥ 3)	
FGFR Alteration Type	
FGFR Gene Type	
Tumor Histology Type	

*Baseline performance status (Eastern Cooperative Oncology Group (ECOG) for adults (≥ 18 years of age), Lansky Score for adolescents (≥ 6 to < 16 years of age), Karnofsky Score for adolescents (≥ 16 to < 18 years of age))

Note that the baseline clinical laboratory tests may not be provided for interim analyses or may be provided by request.

4.2. Disposition Information

The number of subjects in the following disposition categories will be summarized:

- Subjects receiving study agent
- Subjects completed the study

- Subjects who discontinued study agent
- Reasons for discontinuation of study agent
- Subjects who terminated study prematurely
- Reasons for termination of study

A listing of subjects will be provided for the following category:

- Subjects who discontinued study agent

4.3. Treatment Compliance

Relative dose intensity will be summarized descriptively to reflect study agent compliance.

Relative dose intensity will be calculated as follows:

Relative dose intensity (%) = (actual number of dose taken/total number of doses prescribed) x100.

4.4. Extent of Exposure

Descriptive statistics (N, mean, SD, median, and range [minimum, maximum]) for treatment duration, treatment duration excluding dose interruption period, cumulative total dose, and dose intensity will be presented for the safety analysis set and/or the Treated Population in the Broad Panel Cohort. Treatment duration for the study will be calculated as date of last dose of study drug – date of first dose of study drug + 1. Treatment duration excluding dose interruption period are defined as the total number of days that study agent has been administered to the subject (excluding days of study agent interruption).

The number (%) of subjects with a dose adjustment (reduction, interruption, up-titration, re-escalation) will be summarized. Reasons for dose adjustments will also be summarized. Total number of doses skipped and maximum duration of dose skip (days) will also be provided.

4.5. Protocol Deviations

In general, the following list of major protocol deviations may have the potential to impact subjects' rights, safety or well-being, or the integrity and/or result of the clinical study. Subjects with major protocol deviations will be identified prior to database lock and the subjects with major protocol deviations will be summarized by category.

- Developed withdrawal criteria but not withdrawn
- Entered study but did not satisfy entry criteria
- Received a disallowed concomitant treatment
- Received wrong treatment or incorrect dose
- Other

A listing of all major protocol deviations will be provided.

4.6. Concomitant Medications

For summarization purposes, concomitant medications will be coded to generic terms using the World Health Organization Drug Dictionary (WHO-DD). According to the protocol, concomitant therapies must be recorded at the time of full-study screening, during the study, and up to 30 days after the last dose of study drug. Concomitant medications used on or after the same day as the first dose of study treatment, including those that started before and continued after the first dose of study treatment will be summarized.

Summaries of concomitant medications will be presented by Anatomical Therapeutic Chemical (ATC) class and drug generic term. The proportion of subjects who receive each concomitant medication will be summarized.

